3.2 Secondary objective

To assess the safety of Esflurbiprofen Hydrogel Patch compared with placebo applied once a day for up to seven days.

4 Study design

This is a Phase II randomized, double-blind, 2-arm (1:1) (stratified by center and subgroup), multi-center, placebo-controlled, parallel group study of the efficacy and safety of Esflurbiprofen Hydrogel Patch applied once a day for up to 8 days (maximum of 7 patches) to treat acute blunt, soft tissue injuries of the limbs.

To qualify, patients must experience acute blunt, soft tissue injuries of the limbs. Patients should be randomized as soon as possible after the injury. Anticipated time from injury until initial treatment should not exceed 6 hours.

In order to ensure at least 90 evaluable patients per group, up to 200 patients (100 in each group)

Approximately 200 patients suffering from acute blunt, soft tissue injuries of the limbs are to be randomized to be treated with Esflurbiprofen Hydrogel Patch or placebo (assumes a drop-out-rate of $\leq 10\%$).

The study will be performed in Germany in 3 sites. Each site should enroll a minimum of 30 and a maximum of 90 patients.

The first five doses of study drug will be applied at the study site. The patients will be instructed on how to apply the patch once daily at home for the last two treatment days.

After the randomization visit (V1), patients will return to the study center for post-baseline visits V2-V7 to complete efficacy and safety assessments. In addition, patients will assess pain on movement and spontaneous pain intensity at rest at visits 2, 3, 4, 5, 6 and 7.

The schedule of visits is described below.

	Time after initiating treatment	Visit Day
Randomization/Baseline visit V1	0 h	Day 1
1st interim visit V2	12 h (□ 1 h) after V1	Day 1
2nd interim visit V3	24 h (□ 2 h) after V1	Day 2
3rd interim visit V4	48 h (□ 4 h) after V1	Day 3

Table 4–1: Study site visits

Teikoku Chemical Co. Ltd Clinical Study Protocol : TK-254R-0201 Confidential Final Version 3.0

4th interim visit V5	72h (□ 4 h) after V1	Day 4
5th interim visit V6	96 h (□ 4 h) after V1	Day 5
Final visit V7	168 h (□ 24 h) after V1	Day 8 🗆 2day

Rescue medication (paracetamol, 500 mg tablets, up to 3000 mg daily) is allowed during the study, except for the 6 hours prior to V5 (72h).

5 Population

The study population will consist of male or female patients aged 18-60 years with blunt, soft tissue injuries of the limbs.

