6.1 Investigational drug and reference drugs

CLINSEARCH will supply the study drugs and rescue medication (section 6.5.5).

Study drugs will be packed and labelled by CSM, Clinical Supplies Management Europe GmbH.

Esflurbiprofen Hydrogel Patch and the placebo patches are packaged in

. One sachet contains 1 plaster.

The number of IMP units to be packaged will be specified prior to the start of the packaging operations, including units necessary for carrying out quality control and any retention samples to be kept.

The clinical trial supplies will be packed into secondary containers (boxes). Supplies for replacements will be packed separately into further secondary containers.

The IMPs will be labelled in accordance with the GMP Annex 13 and with the GCP regulation ("GCP-Verordnung") § 5.

Investigational drug:

- Active ingredient: Esflurbiprofen Hydrogel Patch containing 165 mg Esflurbiprofen
- □ Excipients:

One unit dose of the drug is one patch applied to the painful area.

Control drug:

Placebo patch that does not contain the active ingredient but is otherwise indistinguishable from the investigational drug Esflurbiprofen Hydrogel Patch.

Rescue medication:

Paracetamol (500 mg tablets, up to 3000 mg daily) is allowed during the study, except for the 6 hours prior to Visit 5 (72h).

6.2 Treatment arms.

Eligible patients will be randomized to one of two treatment arms in a ratio of 1:1

- Esflurbiprofen Hydrogel Patch once a day
- \Box Placebo patch once a day

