In case of a significant result for this first hypothesis two further hypotheses regarding the subgroups "sprains/strains" and "contusions" will be then be also tested by means of the same baseline adjusted ANCOVA model to the 5 % level.

2a) H_{o:} μ_{E(spr/str)}=μ_{P(spr/str)} vs. H₁: μ_{E(spr/str)≠}μ_{P(spr/str)} in the subgroup "Sprains/strains",
2b) H_{o:} μ_{E(con)}=μ_{P(con)} vs. H₁: μ_{E(con)≠}μ_{P(con)} in the subgroup

"contusions". The primary analysis population is the Full Analysis Set (FAS).

Other important secondary efficacy outcomes are pain-on-movement on VAS at 12, 24, 48, 72, 96 and 168 hours after initiating treatment in the FAS population. These will be analyzed with

an analysis-of-covariance (ANCOVA) model and center and subgroup as main effects which will be more detailed described in the Statistical Analysis Plan (SAP). All other continuous efficacy outcomes will be analyzed based on the same model (excluding the baseline covariate when there is no appropriate baseline).

Differences between treatments on categorical outcomes will be tested with Cochran-Mantel-Haenszel tests of treatment mean ridits or of general association, stratified by center.

Figures will show the time course of outcomes by treatment group for key quantitative outcomes. The primary outcome will also be summarized by center (if there is evidence of a treatment-by-center interaction), sex, age and race but without formal statistical comparisons of treatments.

For quantitative outcomes assessed (POM, pain at rest) each null hypothesis will be tested with an analysis-on-covariance (ANCOVA) model including treatment group and center as main effects, and the baseline value as covariate (those outcomes for which there is a baseline). The model will be fit both with and without the treatment-by-center interaction. The primary model will be the model without the interaction. If the treatment/center interaction is statistically significant (p<0.05), additional ANCOVAs will be run to identify the center(s) driving the interaction and to lay out the evidence for efficacy among the centers whose results are concordant and centers driving the interaction. ANCOVA outputs will be presented in the Statistical Appendix for the primary and various secondary outcomes to allow an outside reviewer to assess the acceptability of the primary statistical model.

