2 DESIGN OF THE CLINICAL TRIAL

The study is a Phase II (proof-of-concept), randomized, double-blind, multi-center, placebocontrolled, parallel group clinical trial of the efficacy and safety of Esflurbiprofen Hydrogel Patch applied once a day versus placebo patch applied once a day in the local symptomatic and short-term treatment of pain in acute strains, sprains or bruises of the extremities following blunt trauma, conducted in Germany.

It is planned to include a total of 200 patients (100 patients per active group and 100 per placebo group) in 3 sites.

The duration of each patient's participation in the study will be 7 (+1) consecutive days (from randomization (V1) to Final Visit (V7)).

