For quantitative outcomes assessed (POM, pain-at-rest) each null hypothesis will be tested with an analysis-on-covariance (ANCOVA) model including treatment group and center as main effects, and the baseline value as covariate (those outcomes for which there is a baseline). The model will be fit both with and without the treatment-by-center interaction. The primary model will be the model without the interaction. If the treatment/center interaction is statistically significant (p<0.05), additional ANCOVAs will be run to identify the center(s) driving the interaction and to lay out the evidence for efficacy among the centers whose results are concordant and centers driving the interaction. ANCOVA outputs will be presented in the Statistical Appendix for the primary and various secondary outcomes to allow an outside reviewer to assess the acceptability of the primary statistical model.

CRMB	Trial Substance:	Esflurbiprofen Hydrogel Patch	Study No.: EudraCT No.:	TK-254R-0201 2020-005165-14
	Short Title:	Local symptomatic and short-term treatment of pain in acute strains, sprains or bruises of the extremities following blunt trauma		KU SEIYAKU CO LTD.

The treatment effects will be estimated as mean differences between the active and placebo groups with 95% confidence intervals.

The response outcome (POM reduced by 50% at Visit 5, Yes/No) will be analyzed by the CMH test of general association, stratified by center and also by subgroup.

Differences between treatments in time-to-event outcomes will be tested with the log-rank test stratified by center.

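### If the treatment-by-center interaction reaches p<0.05, the plan runs efficacy ANCOVAs in groups of centers formed by their own results, so the confidence intervals and p-values for those groups are not valid

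*SAP*

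**What the plan says.** The trial plans three sites (Protocol section 4: "The study will be performed in Germany in 3 sites"). SAP 14.4.2 fits the ANCOVA for pain-on-movement and pain at rest with and without a treatment-by-center term, and settles which fit counts: "The primary model will be the model without the interaction". It then adds a conditional step: "If the treatment/center interaction is statistically significant (p<0.05), additional ANCOVAs will be run to identify the center(s) driving the interaction". Protocol 9.7.2 has the same step ("additional ANCOVAs will be run to identify the center(s) driving the interaction"). In both documents a further stated purpose of these extra fits is "to lay out the evidence for efficacy among the centers whose results are concordant and centers driving the interaction".

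Neither document says what makes a center concordant or driving, how many centers may fall in each group, or how the output should be read. The same SAP section says that treatment effects are reported with 95% confidence intervals.

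Two other statements cover the same situation differently. Earlier in SAP 14.4.2 (and in Protocol 9.7.2), the primary outcome is to be summarized by center when an interaction is suspected, with no formal test between treatments. SAP 14.6 promises descriptive statistics for individual sites.

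**The concern.** A center joins the concordant or the driving group because of its observed treatment effect, and that effect is then estimated and tested within the group. An ordinary ANCOVA interval or p-value takes the set of centers as fixed in advance. Once the data have chosen the set, the interval is too narrow and the p-value too small.

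With three centers, a chance interaction would typically leave two that agree and one that does not. The plan would report the two that agree under the heading of evidence for efficacy. At stake is how that supporting result is read, above all when the overall result is weak. The trial's confirmatory conclusion is not at stake.

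**Working it through.** **Inputs from the documents.** Three centers, with limits on their size: "Each site should enroll a minimum of 30 and a maximum of 90 patients" (Protocol section 4). Total size: "It is planned to include a total of 200 patients" (SAP section 2). Allocation: "Eligible patients will be randomized to one of two treatment arms in a ratio of 1:1" (Protocol 6.2). SD 20 mm, difference 10 mm, two-sided 5%, 64 per group for about 80% power, 90 per group planned, 10% dropout (SAP section 6).

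**The plan's own figures.** n per group = 2 × (1.96 + 0.84)² × 20² / 10² ≈ 63. Power with 64 per group is 80.7% (normal approximation) or 80.1% (t-test). 180 / 0.90 = 200. All agree with the SAP.

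**Assumptions.** The split across centers is not given, so 33, 33 and 34 per arm is used as the base case and other splits are tried. The grouping rule is not given either. The base case sets aside the one center furthest from the mean of the other two and pools the remaining pair.

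**Nominal precision.**
- One center of 33 per arm: SE = 20 × √(2/33) = 4.9 mm
- A pair of centers, 66 per arm: SE = 20 × √(2/66) = 3.5 mm
- All centers, 100 per arm: SE = 20 × √(2/100) = 2.8 mm

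**Simulation with no drug effect in any center** (2,000,000 trials, center-level estimates, interaction tested on 2 degrees of freedom at 5%):
- The interaction is significant in 5.0% of trials.
- Among those, the kept pair has two-sided p<0.05 in 31.3%; about 16% favor the drug and about 16% favor placebo.
- As a share of all null trials: 0.050 × 0.313 ≈ 1.6%, of which about 0.8% favor the drug. This is per outcome; the clause covers pain-on-movement and pain at rest at several visits.
- The kept-pair estimate has mean 0.0 mm and SD 6.1 mm, against the nominal 3.5 mm.
- In the same triggered trials the all-center test rejects in 5.0%.
- In 28.8% of triggered trials the pair is significant while the all-center test is not.

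**Sensitivity to the split.** Setting aside the center whose removal leaves least heterogeneity gives 31.8% for 60/60/60 patients, 31.4% for 66/67/67 and for 80/70/50, 30.7% for 90/80/30 and 30.6% for 90/60/30. Refitting the full ANCOVA on simulated patients (60,000 trials per split) gives 30.4% for 60/60/60, 31.6% for 90/80/30 and 32.1% for 67/67/66, with a simulation SE of 0.8 points.

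**Sensitivity to the rule** (triggered null trials, splits within the site limits):

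| Reading of the undefined rule | Two-sided p<0.05 |
|---|---|
| Set aside the center with the largest raw deviation from the overall mean | 20% to 32% |
| Set aside the least favorable center | 23% to 24% |
| Keep the centers with the majority sign | 42% to 45% |
| Keep the centers with the same sign as the overall estimate | 68% to 75% |
| Test the driving center alone | 64% to 66% |
| All centers, model without interaction | 5% to 5.5% |

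**The case against.** The strongest reply is that no planned conclusion rests on this step. The model without the interaction is primary, the confirmatory sequence uses the full analysis set with all centers, and that test keeps its 5% level even in triggered trials. This stands. A reader might infer from 31% that the trial's false-positive rate is inflated; the documents do not support that, because the figure applies only within the 5% of null trials that trigger the clause.

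A reader might also infer a built-in bias in favor of the drug. Looking only at triggered trials where the outlying center is the unfavorable one, the pair shows about +5.4 mm when the truth is 0. The mirror case shows about −5.4 mm, and the average is 0.0 mm. Under the assumed rule the error is excess spread. A rule that always set aside the least favorable center would favor the drug, but neither document states such a rule.

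Third, the plan does not discard a center: it reports the driving centers as well, and sends the ANCOVA output to an appendix so that an outside reader can judge the primary model. That is a fair diagnostic purpose. It does not rescue the intervals and p-values, since both groups are formed by results and the driving center tested alone is significant in 64% to 66% of triggered null trials.

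Finally, SAP 14.4.2 calls tests of secondary variables exploratory. That sentence does not clearly reach this clause, which concerns pain-on-movement and refers to the primary outcome and primary model. The promises of descriptive by-center results elsewhere are real safeguards, but they conflict with a clause that prescribes ANCOVAs for efficacy.

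**Conclusion.** The point holds as a limited one. Intervals and p-values for centers grouped by their own results are not valid, and the clause fits poorly with the descriptive by-center reporting promised in SAP 14.4.2 and 14.6.

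For the kept pair the false-positive rate is about 31% instead of 5%, given a significant interaction and no drug effect; about 16% favor the drug. Over all null trials this is about 1.6%. These figures rest on three centers of similar size, SD 20 mm and an assumed rule that sets one center aside. Splits within the site limits change them little. Other readings of the rule range from roughly 20% to 75%, and none tried comes near 5%.

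The primary test is unaffected. Nothing in the documents gives the grouped analyses a role in the trial's conclusion, so the risk is over-reading of a supporting result.

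**What to change.** Replace the clause in SAP 14.4.2 and Protocol 9.7.2 before unblinding. Suggested content: if the treatment-by-center interaction has p<0.05, the effects in all three centers are shown with 95% confidence intervals from the interaction model, beside the overall effect from the primary model. The center results are labeled descriptive. No pooled estimate, confidence interval or p-value is given for any set of centers chosen by its results. This also brings the clause into line with the by-center summaries planned elsewhere.

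Leave-one-center-out estimates are optional. If they are used, show all three, without p-values, as a descriptive robustness check. With p-values, at least one of the three would be significant in 48% of triggered null trials (24% favoring the drug), so testing them would bring the problem back.

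The cost is one sentence in each document and a few routine model fits. The downside is that no efficacy result for a clean set of centers will be reported.

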14.4.3 Additional exploratory efficacy variables

- •
- Mean adhesion by application site and/or net use.
- If there is significant use of rescue medication, a sensitivity analysis may be performed to assess impact on primary endpoint and responder rate.
- Outcomes will be compared for all use of rescue medication and separately for use to treat blunt trauma. Day 1 and the day of the final visit will count as full days for this purpose. Use of rescue medication on days after study medication has been discontinued will not be counted.
- POM on VAS difference at V4, V5, V6 compared to V1 (BL) (PID V4, PID V5, PID V6) PID V4, PID V5 and PID V6 will be compared between treatment groups using ANCOVA with terms in the model for treatment group, site [as fixed effects], and baseline POM assessment [as a covariate]. Least square mean for each treatment and the corresponding difference between least square means with the p-value and 95 % confidence interval will be presented from the specified ANCOVA model.
- Sum of Pain Intensity differences (SPID) over 0-24, 0-48, 0-72 and 0-96 hours. SPID over 0-24, 0-48, 0-72 and 0-96 hours will be compared between treatment groups using ANCOVA with terms in the model for treatment group, site [as fixed effects], and baseline POM assessment [as a covariate]. Least square mean for each treatment and the corresponding difference between least square means (Active - placebo) with the p-value and 95 % confidence interval will be presented from the specified ANCOVA model.

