- □ intake of long-acting NSAIDs or application of topical medication since the injury (RICE allowed)
- □ participation in a clinical study within 30 days before inclusion in the study or concomitantly
- □ drug or alcohol abuse in the opinion of the investigator
- \Box pregnant and lactating women
- □ women of child-bearing potential without medically accepted contraception
- □ known hypersensitivity to Esflurbiprofen or one of the excipients of the patch
- □ patients with any ongoing condition that may interfere with the absorption, distribution, metabolism, or excretion of Esflurbiprofen
- history of previous significant injury to the same extremity within 6 months
- □ patients with a disease affecting the same limb, such as synovitis, rheumatoid arthritis, arthrosis, etc.
- □ patients having an ongoing painful condition associated with sports-related injury/contusion
- □ patients suffering from symptoms of an infectious disease including swelling of any joint of the affected upper or lower limbs
- □ patients who had surgery of the affected upper or lower limb within one year of study entry
- □ patients with significant diseases (defined as a disease which, in the opinion of the investigator, may either put the patient at risk because of participation in the study or a disease which may influence the results of the study or the patient's ability to participate in the study; includes patients with a history of gastrointestinal bleeding, significant cardiovascular, liver or renal disease).
- \Box patients with a blood coagulation disorder
- □ patients who use any impermissible medication (see below)

Concomitant Treatment 1. Rescue medication

In case of unbearable pain, patients are allowed to take paracetamol tablets (2 x 500 mg). Patients needing more than 6

Confidential Final Version 3.0

tablets (3 g) per day or another drug from the list of impermissible medication will be withdrawn from the study as non-responders. Application of standard care by rest, ice, compression (non-occlusive bandage), or elevation (RICE) can be considered at the

discretion of the Investigator. Also allowed are:

the use of crutches,

elastic, temporary bandages, that could be easily removed to assess the primary variable.

Physiotherapeutic measures (i.e. isomeric exercises to train the muscles) if they don't interact with the injured area

2. Impermissible medication

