6.5.9 Study drug discontinuation and premature patient withdrawal

The study drug must be discontinued and the patient withdrawn from the study if the Investigator determines that continuing it would result in a significant safety risk for that patient. The following circumstances require study drug discontinuation:

- □ Withdrawal of informed consent
- □ Pregnancy
- □ Emergence of any clinically relevant serious adverse events
- Any other protocol deviation that results in a significant risk to the patient's safety

In addition to these requirements for study drug discontinuation, the Investigator should discontinue study drug for a given patient if, on balance, he/she thinks that continuation would be detrimental to the patient's well-being.

Patients may voluntarily withdraw from the study for any reason at any time. They may be considered withdrawn if they state an intention to withdraw, or fail to return for visits, or become lost to follow up for any other reason. If premature withdrawal occurs for any reason, the Investigator must determine the primary reason for a patient's premature withdrawal from the study and this information must be recorded on the Study Completion CRF.

Patients who are prematurely withdrawn from the study will not be replaced.

If a patient is discontinued or decides to withdraw from the study, all evaluations scheduled for the final visit will be performed within one week of study drug discontinuation. Every effort must be made to collect all the required data at the time of patient discontinuation. The Investigator or designee must complete the Study Drug Discontinuation, giving the date and primary reason for stopping the study drug.

For patients who are lost to follow-up (i.e. those patients whose status is unclear because they fail to appear for study visits without stating an intention to withdraw), the Investigator or designee should show "due diligence" by documenting in the source documents the steps taken to contact the patient, e.g. dates of telephone calls, registered letters, etc., in order to establish the reason for discontinuation and to check presence of any AEs.

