The treatment effects will be estimated as mean differences between the active and placebo groups with 95% confidence intervals.

The response outcome (POM reduced by 50% at Visit 5, Yes/No) will be analyzed by the CMH test of general association, stratified by center and also by subgroup.

For ordered categorical outcomes, (the global assessments), differences between treatments will be tested with the CMH test of treatment mean ridits, stratified by center.

Differences between treatments on each quantitative rescue medication outcome will be tested with the CMH test of treatment means, stratified by center.

Differences between treatments in time-to-event outcomes will be tested with the log-rank test stratified by center.

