5.1.2 Secondary efficacy variables

- POM at injured site in mm measured using a 100 mm VAS at 12, 24, 48, 72, 96 and 168 hours after commencement of study treatment and will additionally presented by subgroups (table and Figure).
- AUC over time during first 12, 24, 48, 72, 96 and 168 hours for POM measured using a VAS; ordinate = POM score in mm, abscissa = time after treatment
- Pain-at-rest (PAR) at injured site in mm measured using a 100 mm VAS at 12, 24, 48 72, 96 and 168 hours.
- Reduction in VAS for POM from baseline:
 - Time to meaningful reduction (30%)
 - \circ Time to optimal reduction (50%)
 - Time to complete resolution of pain
- Responder rate 1 (defined as the proportion of patients achieving ≥50% reduction from baseline in the VAS score for POM at 72 hours)
- Responder rate 2 (defined as the proportion of patients able to resume training / normal physical activity by 168 hours)
- Clinical global assessment of efficacy as judged by investigator and patient at 48, 72 and 168 hours
- Overall dose of rescue medication needed (paracetamol).
- POM on VAS by indication at Visit 5.

Additional outcomes

- Adhesive power of patch (5-point scale)
- Mean adhesion by application site and/or net use.
- If there is significant use of rescue medication, a sensitivity analysis may be performed to assess impact on primary endpoint and responder rate.
- Outcomes will be compared for all use of rescue medication and separately for use to treat blunt trauma. Day 1 and the day of the final visit will count as full days for this purpose. Use of rescue medication on days after study medication has been discontinued will not be counted.
- POM on VAS difference at V4, V5, V6 compared to V1 (BL) (PID V4, PID V5, PID V6) PID V4, PID V5 and PID V6 will be compared between treatment groups using ANCOVA with terms in the model for treatment group, site [as fixed effects], and baseline POM assessment [as a covariate]. Least square mean for each treatment and the

CRMB	Trial Substance:	Esflurbiprofen Hydrogel Patch	Study No.: EudraCT No.:	TK-254R-0201 2020-005165-14
	Short Title:	Local symptomatic and short-term treatment of pain in acute strains, sprains or bruises of the extremities following blunt trauma		OKU SEIYAKU CO LTD.

corresponding difference between least square means with the p-value and 95 % confidence interval will be presented from the specified ANCOVA model.

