14.4.2 Secondary efficacy variables

- POM at injured site in mm measured using a 100 mm VAS at 12, 24, 48, 72, 96 and 168 hours after commencement of study treatment and will additionally presented by subgroup (table and Figure).
- AUC over time during first 12, 24, 48, 72, 96 and 168 hours for POM measured using a VAS; ordinate = POM score in mm, abscissa = time after treatment
- Pain-at-rest (PAR) at injured site in mm measured using a 100 mm VAS at 12, 24, 48 72, 96 and 168 hours.
- Reduction in VAS for POM from baseline:
- Time to meaningful reduction (30%)
- Time to optimal reduction (50%)
- Time to complete resolution of pain
- Responder rate 1 (defined as the proportion of patients achieving ≥50% reduction from baseline in the VAS score for POM at 72 hours)
- Responder rate 2 (defined as the proportion of patients able to resume training / normal physical activity by 168 hours)
- Clinical global assessment of efficacy as judged by investigator and patient at 48, 72 and 168 hours
- Overall dose of rescue medication needed (paracetamol).

Statistical test results for secondary variables will only be interpreted exploratorily.

Other important secondary efficacy outcomes are pain-on-movement on VAS at 12, 24, 48, 72, 96 and 168 hours after initiating treatment in the FAS population. These will be analyzed with an analysis-of-covariance (ANCOVA) model and center and subgroup as main effects. All other continuous efficacy outcomes will be analyzed based on the same model (excluding the baseline covariate when there is no appropriate baseline).

Differences between treatments on ordinal outcomes will be tested with Wilcoxon, stratified by center and subgroup.

Figures will show the time course of outcomes by treatment group for key quantitative outcomes. The primary outcome will also be summarized by center (if there is evidence of a treatment-by-center interaction), sex, age and race but without formal statistical comparisons of treatments.

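### The rescue-dose total stops when study drug stops, so a patient withdrawn for heavy rescue use can score better than a moderate user who completes

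*SAP*

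**What the plan says.** - **Outcome.** Protocol 9.7.1 and SAP 5.1.2 and 14.4.2 list "Overall dose of rescue medication needed (paracetamol" among the secondary efficacy variables. It is a total, with no denominator.
- **Counting rule.** Protocol 9.7.1 and SAP 5.1.2 and 14.4.3 carry the same sentence: "Use of rescue medication on days after study medication has been discontinued will not be counted". It excludes later days, not the stopping day itself, and it covers every discontinuation whatever the reason. The sentence before it reads "Day 1 and the day of the final visit will count as full days for this purpose".
- **Withdrawal.** In the protocol synopsis (Concomitant Treatment), patients needing more than 6 "tablets (3 g) per day or another drug from the list of impermissible medication will be withdrawn from the study as non-responders". Protocol 6.5.9 does not list excess rescue among the circumstances requiring discontinuation. For any patient who stops, it says that "all evaluations scheduled for the final visit will be performed within one week of study drug discontinuation".
- **Missing data.** For lack-of-efficacy stops, protocol 9.7.3 and SAP 14.8 give later assessments a worst value and an uncompleted treatment-satisfaction global the worst possible score. These rules concern visits and assessments. None concerns rescue dose.
- **Test.** Protocol 9.7.2: "Differences between treatments on each quantitative rescue medication outcome will be tested with the CMH test of treatment means, stratified by center". The SAP names no test for rescue, which leaves its general rule in 14.4.2: "All other continuous efficacy outcomes will be analyzed based on the same model (excluding the baseline covariate when there is no appropriate baseline". SAP 14.13 promises a later discussion of rescue use, but none follows.
- **Status.** SAP 14.4.2 treats tests on secondary variables as exploratory.

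**The concern.** The event that ends counting can be caused by the quantity being counted. A patient whose pain control fails, and who takes more rescue than the limit, leaves the study and accrues no further dose. The total then ranks this protocol-defined failure as a light user.

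The plan handles the same patient differently elsewhere: after a stop for lack of efficacy, pain scores take a worst value, yet rescue dose keeps whatever small total had accrued. Protocol 7.5.1 also ties the last patch application to resolution of the injury in some patients. A short total can therefore mean healed or failed, and the sum cannot separate them.

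At stake is how a listed secondary variable is read. A lower mean total will be taken as less need for rescue, when part of the difference between arms may reflect who stopped early and why.

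**Working it through.** **1. The plan's own figures.** The documents give no mean, SD, withdrawal rate or power for rescue dose. The only calculation is for the primary endpoint: n = 2 × (1.96 + 0.84)² × 20² / 10² ≈ 63 per group, against 64 stated (exact t-test power at 64 is 80.1%), and 90 / 0.9 = 100 per group, 200 in total. It reproduces and has no bearing on rescue.

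**2. Ordering of patients.** Tablets are 500 mg and the limit is 6 a day.
- Withdrawn on Day 1 after 7 tablets: total 7 (3.5 g), rate 7 per day.
- Completer taking 1 tablet a day on Days 1 to 8: total 8 (4 g), rate 1 per day.
- Completer taking 2 tablets a day: total 16 (8 g), still within the 20 tablets supplied.

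On the total the failure ranks best. On the daily rate it ranks worst.

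**3. Direction of bias.** Let p be the share stopping early in an arm and L the mean uncounted grams per such patient. Then

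change in (placebo − active) caused by truncation = −(p_placebo × L_placebo − p_active × L_active).

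Illustration, every input assumed: patients who stay average 3 g (placebo) and 2 g (active); early stoppers leave on Day 2 after 2.0 + 3.5 = 5.5 g; uncounted use is 1 to 3 g a day for the 6 remaining days, so L = 6 to 18 g.

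Worked row, 10% / 2%: placebo 0.9 × 3 + 0.1 × 5.5 = 3.25; active 0.98 × 2 + 0.02 × 5.5 = 2.07; truncated difference 1.18 g. Counting all days adds (0.10 − 0.02) × 6 = 0.48 up to (0.10 − 0.02) × 18 = 1.44, giving 1.66 to 2.62 g.

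| Stop early, placebo / active | Truncated difference (g) | All days counted (g) | Effect of truncation |
|---|---|---|---|
| 10% / 2% | 1.18 | 1.66 to 2.62 | 29% to 55% smaller |
| 10% / 5% | 1.08 | 1.38 to 1.98 | 22% to 46% smaller |
| 5% / 2% | 1.05 | 1.23 to 1.59 | 15% to 34% smaller |
| 5% / 5% | 0.95 | 0.95 | none |
| 2% / 5% | 0.88 | 0.70 to 0.33 | larger, favours active |
| 2% / 10% | 0.70 | 0.22 to −0.74 | larger, can reverse the sign |

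**4. Tablet supply.** Protocol 6.5.5 provides 20 × 0.5 g = 10 g at Visit 1 and tells patients to take only that supply. In the illustration, at most 10 − 5.5 = 4.5 g remains uncounted. Shrinkage becomes 0.08 × 4.5 / (1.18 + 0.36) = 23% at 10% / 2%, 0.05 × 4.5 / (1.08 + 0.23) = 17% at 10% / 5%, and 0.03 × 4.5 / (1.05 + 0.14) = 11% at 5% / 2%.

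**5. Supply and detection together.** Diaries are reviewed at visits, so excess use is found at the next visit rather than the same day. Simulations with gamma-Poisson daily tablet counts (assumed settings; in one set 100 per arm, with 2% to 6% of active and 8% to 12% of placebo patients withdrawn) gave shrinkage of about 36% to 59% with no cap and same-day withdrawal. With the 20-tablet cap and stopping at the next visit it was about 9% to 13%, and t-test power fell by about 3 points at most.

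**6. Power.** A separate simulation used 90 per arm, 2,000 replicates, gamma totals with means 3 and 2 g, stopping on Days 1 to 4 and 3 g a day uncounted. At 10% / 2%, t-test power was 90.0% truncated and 91.6% with all days counted. At 10% / 5% it was 80.0% and 61.0%. Truncation also removes variance, so a smaller estimate need not mean less power.

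**The case against.** Counting rescue only while on study drug is a legitimate while-on-treatment measure, and a worst-rank composite answers a different question. The counting sentence sits with the additional outcomes, and counting Day 1 and the last day as full days hints at a per-day measure, under which the 7-versus-8 example fails. The sentence is not the main cause either: patients are withdrawn from the study, so later use would mostly go unrecorded. The withdrawal trigger is in the synopsis only. Everything here is exploratory.

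Much of this stands, and it limits the size and severity. It does not remove the point. The listed variable is a total, no denominator is defined, and applying the counting rule to it is the natural reading, because in protocol 9.7.1 the rule closes the section that lists the variable. If a daily rate is intended, the SAP has to say so.

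A reader might infer more: that the rule always biases toward no difference, hides a real rescue-sparing effect and costs power. The documents do not support that. They give no withdrawal rates by arm. The rule also covers stops for drug-related adverse events, which the missing-data rules anticipate and which could be commoner on active. The power results above go both ways.

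**Conclusion.** The point holds as a fault in how the outcome orders patients: truncation depends on the outcome, and an early failure can receive a more favourable total than a moderate user who completes. This follows from the text without any assumed rate, provided the synopsis withdrawal rule is applied.

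The bias in the arm difference is conditional. It is toward zero if early stopping is commoner, or loses more use, on placebo; about nil if stopping and lost use are equal; and in favour of active if stopping is commoner there. With more stopping on placebo, the size runs from roughly 10% (20-tablet supply, withdrawal at the next visit) to roughly 40% to 60% (no cap, same-day withdrawal). All usage and withdrawal rates are assumptions. Power loss is small or uncertain.

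Severity is low to moderate: one secondary variable, tested only exploratorily, with the primary analysis unaffected.

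**What to change.** In the SAP, before unblinding:

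1. Add a rank analysis of rescue dose, stratified by center and subgroup, in which patients who stop for lack of efficacy or excess rescue receive the worst rank. SAP 14.4.2 already names a Wilcoxon test with that stratification for ordinal outcomes. State how patients who stop for other reasons are ranked.
2. Support it with tablets per day on treatment, with the denominator written down.
3. Report early stopping by arm and reason.
4. Keep the truncated total as a descriptive summary.
5. Name one test for rescue in place of the differing protocol and SAP rules.

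The synopsis withdrawal rule and protocol 6.5.9 must be reconciled, since the ranking depends on which patients are withdrawn.

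Deleting the counting sentence alone would not help, because use after withdrawal is mostly not recorded. The proposed analyses need only recorded data. The cost is SAP wording and one additional analysis with its supporting summary. The downside is that the outcome becomes a composite rank rather than a pure dose. It should not be justified by power: in the simulation of step 6, the worst-rank Mann-Whitney test had 84.9% at 10% / 2% and 73.4% at 10% / 5%, below the truncated t-test. The gain is a correct ordering of patients.
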